- To assess the glucose control achieved in adults with type 1 diabetes with the use of the OHSU closed-loop system.
- To assess the tolerability of the PDT glucose sensor.

Study Hypothesis:

We propose that the accuracy of the PDT glucose sensor is not impacted by the delivery of lispro insulin as compared to a saline placebo.

Endpoints**Primary Endpoints**

- Sensor accuracy as determined by mean absolute difference (MAD) for reference YSI venous blood glucose values ≤ 75 mg/dL and mean absolute relative difference for reference YSI venous blood glucose values >75 mg/dL

Secondary Endpoints (duration: entire study):

- Percent of time with sensed glucose between 70 – 180 mg/dl (based on Dexcom G5 CGM)
- Percent of time with sensed glucose <70 mg/dL (based on Dexcom G5 CGM)
- Percent of time with sensed glucose <54 mg/dl (based on Dexcom G5 CGM)
- Percent of time with sensed glucose >250 mg/dL (based on Dexcom G5 CGM)
- Mean sensed glucose (based on Dexcom G5 CGM)
- Number of carbohydrate treatments (defined as 15 or 20 grams of carbohydrate)
- Total amount of insulin delivered (in units/kg)

- Mean score on visual analog scale at 15 and 120 minutes after insertion, and at end of study
- Mean score on Draize scale at end of study

Study Type

This is a single center, one treatment trial designed to compare the sensor accuracy of the PDT sensing catheter when utilized to deliver lispro insulin as compared to a saline control.

Study Population

Study population will be adults with type 1 diabetes, ages 21 – 65 years of age. Younger subjects are excluded as it is appropriate to assess safety first in the adult population. 10 subjects will be recruited to participate in studies.

Power Analysis

Since data have not previously been obtained in humans (variance is unknown), this study is exploratory and not powered.

Protocol Summary:

[figure not shown]
Subjects will undergo one 12 hour inpatient study. During this intervention visit, subjects will wear two t:slim insulin pumps to deliver insulin or saline through two investigational PDT glucose sensing cannulas, and a Dexcom G5 CGM to measure glucose. The subject will come to

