
Stopping Rules

The subject may withdraw at will at any time or at the discretion of the Investigator.

A subject must be withdrawn if any of the following applies:

1. Hypoglycemia: After initial stabilization, one episode of severe hypoglycemia (requiring the assistance of another person) or one episode of venous blood glucose < 50 mg/dl.
2. Hyperglycemia: After initial stabilization, venous blood glucose > 400 mg/dl for over 30 minutes.
3. Ketoacidosis: Venous blood glucose > 250 mg/dl accompanied by serum ketone level > 1.5 mM.
4. Protocol deviation having influence on efficacy or safety data as judged by the Investigator.
5. Substantial and repeated non-compliance with trial procedures
6. Pregnancy
7. Intention of becoming pregnant

The study may be stopped if the glucose sensing cannulas have repeated inability to acquire sensor data, such as telemetry issues.

Data Analysis

Note that it was not possible to carry out a formal sample size power analysis for this feasibility study since data have not previously been obtained in humans (variance is unknown). However, we expect the sample size proposed here (10) is adequate to detect a difference between the insulin formulation and saline, based on our earlier studies in swine. The data obtained in this study will be used to calculate variance so that formal power analyses can be used for subsequent, more formal, studies.

This study design will allow a comparison of sensing accuracy after insulin vs after saline administration through the sensing cannula. For example, this study design will allow assessment of the magnitude of artifact, if any, from the insulin preservatives, as was noted in pig studies with the non-redox mediator sensor. It will also assess the potential for underestimation of glucose due to uptake into fat as a result of local insulin delivery [19], [20].

For each subject, we plan to acquire data from the PDT sensor which is represented by an

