electrical current in nanoamperes (nA). We will match these sensor values with YSI values which are in units of mg/dL. We will then do a linear least squares regression between the YSI glucose and the sensor current to create an equation that estimates the actual glucose from the sensor current. This equation will have the form of $y=mx + b$, whereby y is the estimated glucose (mg/dL), m is the slope (mg/dL/nA), x is the current measured by the sensor (nA), and b is the intercept or background current (nA). The slope and intercept will be estimated for each patient and for both the saline sensing catheters and the insulin sensing catheters. We will then do a t-test between the slopes and the intercepts comparing these values between the saline sensing catheters and the insulin sensing catheters. The hypothesis is that the null hypothesis (the mean value of both the slope and intercept values are identical between the saline and insulin sensing catheters) is true which will be estimated by a p-value being greater than 0.05.

Another key end point will be glucose sensor accuracy (absolute difference, relative difference, and absolute relative difference) during insulin vs during saline delivery. These metrics will be calculated by using two types of calibration schemes: a one-point calibration with fixed offset, performed prospectively before meal administration, as described earlier [21]; and a retrospective all point calibration as proposed for early device evaluation, as proposed by Heinemann and Ludwig [22]. In addition to mean and median absolute difference, mean and median relative difference, and mean and median absolute relative difference, other accuracy metrics will include signed difference (bias). Error grid analyses will include Clarke, Parkes and continuous analyses. Bland-Altman analysis will be used to stratify accuracy as a function of glucose level.

In addition to the glucose sensing data described above, the subjects enrolled in the proposed clinical study will be asked to provide tolerability scores, which will include visual analog scales, to assess their level of comfort. During the study, skin irritation (Draize scores) will also be recorded. The tolerability and Draize scores will provide key data that will be used to support subsequent device modifications that reduce discomfort and skin irritation.

Confidentiality and Protection of Human Subjects

RISKS and BENEFITS

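### The plan treats p > 0.05 on slope and intercept as showing that lispro has no effect, with 10 subjects, no margin and no confidence-interval criterion

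*Combined protocol and SAP*

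**What the plan says.** The Study Hypothesis section proposes that "the accuracy of the PDT glucose sensor is not impacted by the delivery of lispro insulin as compared to a saline placebo". The primary endpoint is sensor accuracy against YSI venous glucose: mean absolute difference (MAD) at or below 75 mg/dL and mean absolute relative difference (MARD) above it.

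The Data Analysis section then regresses YSI glucose on sensor current. "The slope and intercept will be estimated for each patient and for both the saline sensing catheters and the insulin sensing catheters". Slopes and intercepts are compared between catheters by t-test. The null hypothesis is that "the mean value of both the slope and intercept values are identical between the saline and insulin sensing catheters", and the plan expects that this null "is true which will be estimated by a p-value being greater than 0.05".

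A further paragraph adds: "Another key end point will be glucose sensor accuracy (absolute difference, relative difference, and absolute relative difference) during insulin vs during saline delivery". These metrics are to be computed under two calibration schemes, together with signed bias, error grids and Bland-Altman analysis. None has an acceptance limit. No insulin-minus-saline difference with a confidence interval is planned for MAD, MARD or anything else.

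On size, the Power Analysis section says that "this study is exploratory and not powered". The Data Analysis section nevertheless expects 10 subjects to be enough to detect an insulin–saline difference, citing swine studies whose figures are not given.

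**The concern.** A p-value above 0.05 says only that the data did not exclude a zero difference. It does not say that the difference is small. Using it as the test of a no-difference hypothesis reverses the usual incentive: fewer subjects, lost sensor traces or noisier calibration all make the favourable answer more likely. Data loss is a live possibility, since the Stopping Rules say: "The study may be stopped if the glucose sensing cannulas have repeated inability to acquire sensor data, such as telemetry issues".

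The rule also carries more weight than its place in the text suggests. The listed primary endpoint has no between-catheter inference of its own. The p > 0.05 criterion is therefore the only inferential basis in the document for the claim that lispro leaves the sensor unaffected. Sensor readings from the investigational cannulas never drive insulin dosing, so what is at stake is a wrong conclusion on the primary objective and not a dosing risk.

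**Working it through.** **Inputs from the document.** 10 subjects (Study Population); one insulin and one saline estimate per subject; threshold 0.05; variance stated to be unknown. The figure of 10 cannot be reproduced, because no effect size, SD, power or margin is given.

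**Assumptions.** Two-sided test. Paired analysis, which the within-subject data call for but the plan does not state. True differences δ are in units of SDd, the true SD of the within-subject difference.

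**Step 1: one parameter.** With T a noncentral t variable on n − 1 degrees of freedom and noncentrality δ√n,

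P(p > 0.05) = P(−t* < T < t*), where t* = t(0.975, n − 1).

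For n = 10, t* = 2.262, and δ = 0.5 gives noncentrality 0.5 × √10 = 1.58.

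| Pairs | True difference (SDd) | P(p > 0.05) |
|---|---|---|
| 10 | 0.5 | 0.707 |
| 10 | 0.7 | 0.494 |
| 10 | 1.0 | 0.197 |
| 8 | 0.5 | 0.768 |
| 6 | 0.5 | 0.829 |
| 4 | 0.5 | 0.889 |
| 20 | 0.5 | 0.435 |
| 40 | 0.5 | 0.131 |

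Only the 10-pair rows describe the plan as written. The other rows show the direction: the smaller the sample, the more often the rule passes. Noise acts the same way. A difference of 1.0 SDd becomes 0.5 of the new SD if the SD doubles, and the pass rate rises from 20% to 71%.

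An unpaired test of 10 against 10 would pass 82% of the time at 0.5 and 44% at 1.0, in units of the common SD.

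**Step 2: the joint rule.** The stated null covers slope and intercept together, so the rule passes when both are non-significant. Under independence the rates follow from Step 1:

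- One shifted by 0.5 SDd: 0.707 × 0.95 = 0.672.
- Both shifted by 0.5 SDd: 0.707² = 0.500.

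Simulation (400,000 runs, 10 pairs, assumed correlation between the two differences of 0, −0.5 and −0.8) gives these ranges:

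| True shift (SDd) | One parameter shifted | Both shifted equally, same or opposite sign |
|---|---|---|
| 0.5 | 67–68% | 44–61% |
| 0.7 | 47% | 16–38% |
| 1.0 | 18–19% | 1–12% |

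Positive correlations of the same size only exchange the same-sign and opposite-sign cases. The rule passes more than half the time below about 0.67 SDd when one parameter is shifted. When both are shifted, that point lies between about 0.46 and 0.60 SDd.

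**Step 3: what a non-significant result leaves open.** The paired 95% interval half-width is t(0.975, 9)/√10 = 2.262/3.162 = 0.715 of the observed SD. Even an observed difference of exactly zero leaves true differences up to about 0.72 observed SD inside the interval. An observed difference just short of significance leaves up to about 0.715 + 0.715 = 1.43.

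**Step 4: what a proper equivalence claim would need.** Two one-sided tests at 0.05 (90% interval inside the margin), true difference zero, 10 pairs, one quantity: power is 6.5% at a margin of 0.5 SDd, 51.6% at 0.8 and 79.5% at 1.0. For 80% power, the pairs needed are 36, 15 and 11. If slope and intercept must both pass at 1.0 SDd, power is 0.795² = 0.632 under independence, and 0.658 and 0.702 at correlations of −0.5 and −0.8.

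**The case against.** The strongest reply is that this is a 10-subject feasibility study, labelled exploratory, meant to supply variance for later work. The primary objective is to assess the impact of lispro, not to prove there is none. The Data Analysis section speaks of gauging the size of any preservative artifact, and Appendix C ties success to how well the sensor tracks blood glucose. Bias, error grids and Bland-Altman plots will sit beside the p-value. The t-test concerns calibration parameters, not the listed MAD/MARD endpoint, and no sentence says in terms that it settles the Study Hypothesis. Lost visits may be repeated, and up to 25 people may be screened for 10 places. All the effect sizes above are in units of an unknown SD.

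Much of this is fair as context. Slope and intercept are not the listed endpoint. The repeat visit, though optional, reduces data loss. The 4-, 20- and 40-pair figures are illustrations only. Without a variance, nobody can say what 0.5 SDd means in mg/dL/nA, and effects above about 1 SDd would mostly be detected.

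None of it supplies another decision rule. The exploratory label excuses the sample size, not the inference: an unpowered study is where p > 0.05 says least. The tracking statement and the descriptive metrics have no limits and no between-catheter interval, so the p > 0.05 sentence remains the only stated route to a conclusion.

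**Conclusion.** The concern holds. The rule is wrong as written, not merely short of detail, and it should be changed before the data are analysed. With 10 complete pairs and a true shift of 0.5 SDd, the plan would accept identity about two times in three if one parameter is affected, and 44–61% of the time if both are. These figures rest on a two-sided paired test, an assumed correlation of 0 to −0.8, and effects scaled to an SD the document does not give. The flaw itself depends on none of these assumptions, because no choice of SD makes non-significance evidence of equality.

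Three smaller points go with it. The Background section also words its hypothesis as the absence of a significant difference. The t-test is not described as paired. The expectation that 10 subjects can detect a difference is undocumented here and fits awkwardly with the statement that the study is not powered.

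**What to change.** 1. Delete the p > 0.05 rule from the Data Analysis section.
2. Replace it with text such as: *The within-subject insulin-minus-saline mean difference will be reported with its 95% confidence interval (paired analysis) for slope, intercept, MAD (YSI ≤ 75 mg/dL) and MARD (YSI > 75 mg/dL), the last two under each planned calibration scheme, with the number of contributing subjects for each.* Keep the planned descriptive metrics.
3. Some subjects may have no YSI value at or below 75 mg/dL. Set in advance the number of contributing subjects below which MAD values are only listed individually. The interval half-width is 1.049 observed SD at 6 subjects and 1.591 at 4.
4. State that no claim of equivalence or absence of impact will be drawn from non-significance. If such a claim is wanted, justify a margin for each quantity before data are seen and require its 90% interval to lie inside it.

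Minor edits: align the Background wording, call the test paired, and delete the sample-size expectation or mark it as undocumented. If a figure replaces that expectation, limit it to slope and intercept with 10 complete pairs: 80% power for a true difference of about 1.0 SDd, and a 95% half-width of about 0.72 of the observed SD.

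The cost is wording and a few lines of analysis, with no added subjects, visits or measurements. The real price is a less favourable conclusion. Ten pairs give about 80% equivalence power for one quantity only at a margin near 1.0 SDd, so estimation without an equivalence claim is the likely outcome. That still meets the study's stated aim of providing variance for later trials.

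### The primary endpoint (MAD/MARD) has no planned paired estimate, confidence interval or primary calibration scheme; the only decision rule, p > 0.05, is on slope and intercept

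*Combined protocol and SAP*

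**What the plan says.** Primary Endpoints lists a single item, accuracy against YSI: MAD for reference values at or below 75 mg/dL and MARD above that. Study Hypothesis and Study Type are both worded as accuracy. Primary Objectives is broader: the effect of lispro on glucose sensing. Power Analysis calls the study exploratory and unpowered.

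Data Analysis first states the contrast: "This study design will allow a comparison of sensing accuracy after insulin vs after saline administration". It then regresses YSI on sensor current for each subject and catheter, and continues: "We will then do a t-test between the slopes and the intercepts". The stated expectation is that the null is true, "which will be estimated by a p-value being greater than 0.05". Slope and intercept appear in neither the primary nor the secondary endpoint list.

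Accuracy follows: "Another key end point will be glucose sensor accuracy", compared between insulin and saline delivery. "These metrics will be calculated by using two types of calibration schemes": a one-point scheme with fixed offset, "performed prospectively before meal administration", and "a retrospective all point calibration as proposed for early device evaluation". Means, medians, signed bias, three error grids and Bland-Altman are listed. No between-catheter difference, SD, interval or pairing is given. Neither scheme is called primary, and the 75 mg/dL split is not carried over.

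On later studies the section says: "The data obtained in this study will be used to calculate variance". It does not say of which quantity.

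**The concern.** The quantity the hypothesis is about and the quantity that carries the decision rule are different. Slope and intercept describe the calibration line. MARD and MAD describe the error left after calibration. One can change without the other.

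Two things are at stake. First, the only yes/no statement the plan produces is a non-significant t-test on 10 subjects, read as proof of the null. If that is carried over to the accuracy hypothesis, the conclusion is unsound. Second, the primary endpoint itself would be reported without a between-catheter estimate or its uncertainty, under a calibration scheme that could be chosen after the results are known. Every subject wears both catheters, so the SD of the paired difference in the endpoint is what a later power calculation for this comparison needs. The plan does not name it.

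**Working it through.** The plan has no calculation to reproduce: no effect size, SD, power or margin is given.

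**1. Inputs from the documents.** 10 subjects, each with both catheters, so 10 pairs. Closed loop starts at 9:30, with samples every 15 minutes until 18:00: (18.0 − 9.5) × 4 + 1 = 35 readings per subject.

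**2. What p > 0.05 can show with 10 pairs.** Noncentral t, two-sided 5%, paired: a true difference of 0.5 SD gives p > 0.05 in 71% of trials, 0.8 SD in 38%, 1.0 SD in 20%. Power of 80% needs 1.00 SD paired or 1.32 SD unpaired; the plan does not say which test is meant. With no difference at all, two independent tests both give p > 0.05 in 0.95 × 0.95 = 90.25% of trials.

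**3. Slope can change while all-point accuracy does not.** A least-squares fit of YSI on current gives the same fitted values after any linear rescaling of the current. Example with eight readings (60 to 250 mg/dL) and background 2 nA: cutting gain from 0.10 to 0.075 nA per mg/dL moves the slope from 10.30 to 13.73 (ratio 1/0.75 = 1.33). MARD stays at 4.72% and MAD at 1.44 mg/dL.

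**4. Simulation.** Every sensor and glucose parameter is an assumption:
- Glucose AR(1), correlation 0.9, mean 160 mg/dL, SD 40 or 50, the same series for both catheters.
- Current = background + sensitivity × (glucose + noise), noise SD 10 mg/dL unless changed.
- Sensitivity 0.10 nA per mg/dL, log-SD 0.1 to 0.3; background mean 2 nA, SD 0.5 or 2.
- One-point calibration at 10:45 with a 2 nA offset, scored on later readings.
- Paired t-tests. The rule passes when both p-values exceed 0.05.

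| Change in insulin catheter | All-point MARD | Rule passes | Paired CI excludes zero, all-point | Same, one-point |
|---|---|---|---|---|
| None | 4.8-4.9% in both | 90-92% | – | – |
| Noise 10 to 13 mg/dL | about 4.9% to 6.1% | roughly 40-85% | about 90% | 12-25% |
| Noise 10 to 16 mg/dL | about 4.9% to 7.3% | 3-60% | about 100% | 33-58% |
| 20% sensitivity loss after calibration | 4.9% to 7.4% | roughly 35-75% | over 99% | 81-98% |
| 20% sensitivity loss from the start | 4.8-4.9% in both | flags 97-98%, 58-60%, 33-34% at log-SD 0.1, 0.2, 0.3 | – | – |

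**5. Precision of the proposed estimate.** Half-width of the 95% CI = t(0.975, 9)/√10 × SD = 0.715 × SD of the paired differences. For assumed SDs of 3, 5 and 8 MARD points that is ±2.1, ±3.6 and ±5.7 points. In the simulation with no difference, the median half-width was 0.63-0.67 points under all-point and 2.93-4.55 under one-point. Mean one-point MARD was about 7.7-8.3% at background SD 0.5 nA. At 2 nA it was about 9-16% and unstable, because the calibration denominator can approach zero.

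**6. The low-glucose stratum.** The same model gives 0.56-1.60 readings at or below 75 mg/dL per subject, so about 6-16 in all, from about 2-4 of 10 subjects. It does not model closed-loop control, meals or carbohydrate treatment.

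**The case against.** The strongest reply is that this is a declared exploratory, unpowered feasibility study. It already plans an insulin-versus-saline accuracy comparison with many metrics, under both calibration schemes. The p > 0.05 rule is worded about slope and intercept only. Much of this stands, and it rules out several stronger readings:

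- *That the plan ignores accuracy.* It does not. The descriptive comparison is there; the paired difference and its uncertainty are missing.
- *That the rule is the formal test of the accuracy hypothesis.* The text does not say so. The harm arises if it is read that way, which is easy because it is the only decision rule and the hypothesis is one of no impact.
- *That flagging a stable sensitivity loss is a false alarm.* It is not. Primary Objectives asks about sensing, and Data Analysis wants the size of any preservative artefact. The two analyses answer different questions.
- *That all-point calibration should be primary.* It does better in the noise and late-loss scenarios, but it cannot show a stable gain or offset shift.
- *That both schemes absorb a loss present from the start.* This is exact for all-point. It is not secure for one-point when background current varies.

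The simulation inputs are also open to challenge. A background mean and SD both of 2 nA implies negative background in about 16% of catheters, and pass rates over the three accuracy-loss scenarios run from 3% to 85%. A large noise rise with low background variability is usually caught.

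Exploratory status does not answer the point. An estimate with an interval is what an exploratory study should report, and the plan itself sets a p-value rule and expects 10 subjects to be adequate to detect a difference.

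**Conclusion.** The point holds as a mismatch in the text, and that part needs no assumption: the primary endpoint has no specified between-catheter estimate, SD, interval or primary calibration scheme, while the sole decision rule sits on unlisted quantities and treats non-significance as proof. That 10 pairs cannot support a no-difference claim in this way follows from the sample size alone (71% non-significant at a true difference of 0.5 SD on a single test).

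How often the rule would miss a real accuracy loss rests wholly on the assumed sensor model: roughly 40-85% for a moderate noise rise and 35-75% for a late 20% sensitivity loss. These figures show that the disagreement can be large; they do not predict this device. The advantage of the paired interval also depends on the scheme: for the moderate noise rise it is clear under all-point and weak under one-point. The documents do not support calling the study invalid, requiring a powered test, or preferring either scheme. The wording should be changed before the data are analysed.

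**What to change.** In Data Analysis:

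1. State the primary analysis: for each subject and catheter, calculate MARD (YSI above 75 mg/dL) and MAD (YSI at or below 75 mg/dL); report the paired insulin-minus-saline difference with mean, SD and 95% CI across subjects. Give the number of readings and of subjects behind the MAD.
2. Name one of the two planned calibration schemes as primary before the data are seen, and report the other beside it. The choice is the investigators': all-point is fitted to the readings it is judged on and hides stable shifts; one-point gives a much wider interval and an unstable mean when background current varies.
3. Keep slope and intercept as supportive measures of sensor response, reported as paired differences with 95% CI. Delete the rule that p > 0.05 shows the null to be true.
4. Present the result as an estimate, in keeping with the exploratory status, and name the SD of the paired difference as the variance to carry into later power calculations.

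The cost is wording only, with no new data or visits. The downsides are a less definite conclusion than no difference, and a MAD at or below 75 mg/dL that may rest on too few readings for a useful interval.
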